- 4 Ultrasound – Thickness of fat will be obtained by ultrasonic measurements across target area. Abdominal or thigh ultrasound will be performed at Screening, Day 1, and Week 4. Abdominal or thigh ultrasound may be performed within 4 days before Day 1 and up to 4 days before/after Week 4 follow-up visit. Day 1 ultrasound can be exempted if the screening ultrasound is performed within 4 days prior to IP dose, and the screening ultrasound can be accepted as the Baseline value.
 - 5 A complete physical examination will include, at a minimum, assessments of the cardiovascular, respiratory, gastrointestinal, and neurological systems.
 - 6 On Day 1, injection site assessments will be performed pre-dose and at 1-hour post-dose.
 - 7 On Day 1, vital signs assessments to be performed pre-dose and at 1-hour post-dose. Vital sign assessments include temperature, pulse rate, blood pressure, and respiratory rate. At simultaneously scheduled assessments, vital signs will be collected prior to any blood draws.
 - 8 On Day 1, ECG assessments will be performed pre-dose only. ECG to be performed in supine position after at least 5 minutes rest. The following ECG parameters will be recorded: heart rate, RR interval, PR interval, QT interval, QTc interval, and QRS interval.
 - 9 Blood tests include biochemistry, hematology, and coagulation assessments. Biochemistry assessments include albumin, ALT, AST, ALP, triglyceride, total cholesterol, LDL-C, HDL-C, TBIL, GGT, urea, creatinine, eGFR, HbA1c, FBS, Sodium, Potassium, Bicarbonate, and Chloride. Hematological assessments include Hb, Hct, RBC count, mean corpuscular volume, Leukocyte/white blood cell (WBC) count, WBC differential, and platelet count. Coagulation assessments include aPTT, Prothrombin time, and INR.
 - 10 Urinary samples for dipstick will be collected. On Day 1, collection will be performed pre-dose only.
 - 11 Serum β -hCG test will be taken for WOCBP at Screening visit only. FSH test is required for females who are post-menopausal at the Screening visit. Urine β -hCG strip test will be taken WOCBP for other scheduled visits.
 - 12 Virology tests include HIV/HBV/HCV infection test. Active HIV infection is detected by detectable positive HIV Ag/Ab combo test; active HBV: HBsAg; active HCV: positive anti-HCV antibody.
 - 13 On Day 1, photography will be performed pre-dose and at 1 hour post-dose on Day 1. Other timepoints on Day 1 can be added to record the ISR at the discretion of the Investigator.

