 - ² Anthropometric parameters include body height, body weight and abdominal skinfold thickness measured by caliper. Body weight will be measured at all visits to calculate the BMI. Body height and abdominal skinfold thickness (by caliper) will be measured at Screening only.
 - ³ Ultrasound – Thickness of fat will be obtained by ultrasonic measurements across target area. Abdominal ultrasound will be performed within 4 days before Visit 2 (Day 1), Visits 3, 4 and 5; and 4 days before/after the follow-up visits.
 - ⁴ A complete physical examination will include, at a minimum, assessments of the cardiovascular, respiratory, gastrointestinal, and neurological systems and will be performed pre-dose.
 - ⁵ On Visit 2 (Day 1), Visit 3, Visit 4, and Visit 5, the injection site assessments will be performed pre-dose and post-dose. Subjects will document any change to the ISRs in between visits in the Subject Diaries.
 - ⁶ On Visit 2 (Day 1), Visit 3, Visit 4, and Visit 5, vital signs assessments to be performed pre-dose. Vital sign assessments include temperature, pulse rate, blood pressure, and respiratory rate.
 - ⁷ On Visit 2 (Day 1), ECG assessments will be performed pre-dose. ECG to be performed in supine position after at least 5 minutes rest. The following ECG parameters will be recorded: heart rate, RR interval, PR interval, QT interval, and QRS interval.
 - ⁸ Blood tests include biochemistry, hematology, and coagulation assessments. Biochemistry assessments include albumin, ALT, AST, ALP, triglyceride, total cholesterol, LDL-C, HDL-C, TBIL, GGT, urea, creatinine, eGFR, HbA1c, FBS, Sodium, Potassium, Bicarbonate, and Chloride. Hematological assessments include Hb, Hct, RBC count, mean corpuscular volume, WBC count, WBC differential, and platelet count. Coagulation assessments include aPTT, Prothrombin time, and INR.
 - ⁹ Urinary samples for dipstick will be collected.
 - ¹⁰ Serum β -hCG test will be taken for WOCBP at Screening visit only. FSH test is required for females who are post-menopausal at Screening visit. Urine β -hCG strip test will be taken for WOCBP for other scheduled visits.
 - ¹¹ Virology tests include HIV/HBV/HCV infection test. Active HIV infection is detected by detectable positive HIV Ag/Ab combo test; HBV: HBsAg; HCV: positive anti-HCV antibody.

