 - ¹² On Visit 2 (Day 1), Visit 3, Visit 4, and Visit 5, the photography will be performed pre-dose. The post-dose photography will be performed only when any severe or unusual ISR was observed and assessed by Investigator after IP administration.
 - ¹³ The occurring AEs/SAEs (including AESI) will be followed until resolution or the event is considered stable.

- ¹⁴ On follow-up visits, no subject diary will be provided to subjects and only review and recording of subject dairy entries will be conducted.
- ¹⁵ Collected only if a medication is related to AEs following the Visit 6
- ¹⁶ Assessment/collection can be performed on or within 4-days window prior to visit date.
- ¹⁷ Eligible subjects will be randomly assigned to either the CBL-514 group or placebo group at a ratio of 2:1.
- ¹⁸ ECG assessment can be performed on or within 4 days before or after Visit 6/ET

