14.1.7. Laboratory Assessments

Safety laboratory tests (hematology, coagulation, biochemistry, urinalysis [dipstick]) will be performed at the time points specified in the study schedules ([Table 4](#) and [Table 5](#)). Additional clinical laboratory tests may be performed at other times if deemed necessary based on the subject's clinical condition.

Medically indicated laboratory tests (emergency or unscheduled tests) should be conducted at the local laboratory.

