3.1 General Considerations

All data collected on the electronic case report form (eCRF) will be presented in the data listings and will be listed and sorted by treatment arm participant number and visit, where applicable. All descriptive summaries will be presented by treatment group and nominal visit/time point (where applicable).

Unless otherwise stated, the following methods will be applied:

- Continuous variables: Descriptive statistics will include the number of non-missing values (n), arithmetic mean, standard deviation (SD), median, minimum and maximum values.

The minimum and maximum values will be displayed to the same decimal precision as the source data, the arithmetic mean, SD and median values will be displayed to one more decimal than the source data for the specific variable.

95% Confidence Intervals (CIs), mean differences (among treatments and from baseline) and least-square (LS-Means) values will be displayed to one more decimal than the source data for a specific variable. P-values will be displayed to 5 decimal places.

The appropriate precision for derived variables will be determined based on the precision of the data on which the derivations are based, and statistics will be presented in accordance with the above mentioned rules.

- Categorical variables: Descriptive statistics will include counts and percentages per category. The denominator in all percentage calculations will be the number of participants in the relevant analysis population with non-missing data, unless specifically stated otherwise. Percentages will be displayed to one decimal place. Proportions will be displayed to 3 decimal places.

95% Confidence Intervals (CIs), difference in proportions, and other categorical parameters will be displayed to one decimal place for percentages. Proportions will be displayed to 3 decimal places. P-values will be displayed to 5 decimal places.

- Repeat/unscheduled assessments: Only values collected at scheduled study visits/time points will be presented in summary tables. If a repeat assessment was performed, the result from the original assessment will be presented as the result at the specific visit/time point. All collected data will be included in the data listings.
- Assessment windows: All assessments will be included in the data listings and no visit windows will be applied to exclude assessments that were performed outside of the protocol specified procedure windows.

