3.2 Key Definitions

The following definitions will be used:

- Subcutaneous Fat Thickness: Subcutaneous fat thickness can be calculated by the mean of ultrasound results of subcutaneous fat thickness at 4 ultrasound scan spots on abdomen including far left, left, far right, and right spots:

$$\text{Subcutaneous Fat Thickness} = [\text{Ultrasound Result (Far Left)} + \text{Ultrasound Result (Left)} + \text{Ultrasound Result (Right)} + \text{Ultrasound Result (Far Right)}] / 4$$

- Subcutaneous Fat Volume:
 - Stage 1: Subcutaneous fat volume over treated area for each treatment group in Stage 1 will be calculated using the following formulas as suggested in the previous Caliway studies:

$$\text{CBL-514 480 mg: Subcutaneous Fat Volume(mL)} = \text{Subcutaneous Fat Thickness(cm)} \times 240 \text{ cm}^2$$

$$\text{CBL-514 640 mg: Subcutaneous Fat Volume(mL)} = \text{Subcutaneous Fat Thickness(cm)} \times 320 \text{ cm}^2$$

$$\text{CBL-514 800 mg: Subcutaneous Fat Volume(mL)} = \text{Subcutaneous Fat Thickness(cm)} \times 400 \text{ cm}^2$$

- Stage 2: Assuming the treatment area is 300 cm² (which is the area for the maximum dose of 50 injections) subcutaneous fat volume over treated area will be calculated using the following formula as suggested in the previous Caliway studies:

$$\text{Subcutaneous Fat Volume(mL)} = \text{Subcutaneous Fat Thickness(cm)} \times 300 \text{ cm}^2$$

- Baseline: The baseline value is defined as the last available valid (quantifiable continuous or categorical value), non-missing observation for each participant prior to first study drug administration. Repeat and unscheduled assessments will be included in the derivation of the baseline values.
- Change from Baseline: The change from baseline value is defined as the difference between the result collected/derived at a post-baseline visit/time point and the baseline value.

The change from baseline value at each post-baseline visit/time point will be calculated for all continuous parameters using the following formula:

$$\text{Change from Baseline Value} = \text{Result at Visit/Time Point} - \text{Baseline Value}$$

- The change of subcutaneous fat thickness and fat volume from baseline value at a post-baseline visit/time point will be calculated using the following formulas:

$$\text{Change of Subcutaneous Fat Thickness from Baseline Value} = \text{Subcutaneous fat thickness value at Visit/Time Point} - \text{Subcutaneous fat thickness value at Baseline}$$

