18. LDL-C

19. HDL-C

Coagulation:

20. International Normalized Ratio (INR)

21. Activated Partial Thromboplastin Time (aPTT)

22. Prothrombin Time.

Urinalysis & Microscopic Urinalysis:

A urinalysis test (dipstick) will be performed for each subject. If clinically significant abnormality is noted for protein, blood, or leukocyte esterase (and at the discretion of the Investigator) a microscopic examination of RBC, WBC, bacteria, and casts will be performed.

All laboratory data collected at scheduled and unscheduled visits will be included in the listings, but only results collected as scheduled visits will be included in the summary tables.

Results for individual parameters may be reported in different units depending on the analyzing laboratory. If required, the results (and the corresponding normal range cut-off values) for individual parameters may be converted to International System of Units (S.I.) units to summarize the data.

For all the parameters where a unit value has been reported, the parameter names that will be used in the outputs will comprise of the test name and the unit of measure, for example, 'Albumin (g/L)'. For the urinalysis parameters, the parameter name will be the reported test name only. Parameters will be sorted alphabetically within tables and listings.

For all parameters where a normal range limit value was reported, the normal range will be derived based on the available lower and upper limit values and any reported mathematical symbols. If both a lower and upper limit value is available, the normal range will be presented as '(Lower, Upper)'.

The reported results for each parameter with a defined normal range will be classified ('Low', 'Normal', 'High') in relation to the defined normal range limits. If a result is equal to the normal range cut-off value, the result will be considered 'Normal'.

The hematology and chemistry results tables will present summary statistics for each laboratory parameter within the specific test panel. For each parameter, summaries will be presented for the baseline and each scheduled post-baseline visit. In addition, summaries will be presented for the change from baseline values at each scheduled post-baseline visit (continuous descriptive analysis).

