The change from baseline values at each post-baseline visit will be calculated for all parameters with continuous results (except for pH and Specific Gravity). The abnormal urinalysis result (dipstick and microscopy), if applicable, will be listed only.

The decimal precision to which the summaries for each parameter will be based on the maximum number of decimals to which the reported result or the normal range limits are presented to in the raw data. The results and normal ranges will be displayed to the same decimal precision in the listings.

Additionally, counts (%) of number participants with values out of normal range at each scheduled time point will also be presented along with shift tables that will represent the changes in normal range categories across post-baseline time points (categorical descriptive analysis).

The urinalysis table will present counts and percentages of normal, abnormal clinically significant and clinically significant for the reported results at baseline and each post-baseline visit for all parameters (categorical descriptive analysis).

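### Stage 2 laboratory tables omit unscheduled post-baseline results, so a transient post-dose abnormality not reported as an adverse event appears only in listings

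*SAP*

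**What the plan says.** **Table rule.** SAP 3.1 sets the general rule: "Only values collected at scheduled study visits/time points will be presented in summary tables". If a test is repeated, the first result is the one tabulated. SAP 11.2 applies this to laboratory data ("only results collected as scheduled visits will be included in the summary tables"), and SAP 11.3 has the same rule for vital signs. For laboratory parameters, SAP 11.2 adds counts of participants with "values out of normal range at each scheduled time point will also be presented along with shift tables". SAP 3.1 sends all collected data, including unscheduled and repeat results, to the listings. Baseline is treated differently in SAP 3.2: "Repeat and unscheduled assessments will be included in the derivation of the baseline values".

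**Stage 2 sampling.** Protocol Table 5, footnote 6, has "vital signs assessments to be performed pre-dose" at Visits 2 to 5. Section 12.2.3.1 puts blood tests and vital signs for Visits 3 to 5 in the list of procedures before dosing. The after-dosing lists (12.2.2.3 and 12.2.3.3) contain neither. Footnote 16 adds: "Assessment/collection can be performed on or within 4-days window prior to visit date". The last routine set is at Visit 6, and Visit 7 has none. Unscheduled tests are allowed; Protocol 14.1.7 says "Additional clinical laboratory tests may be performed at other times if deemed necessary".

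**Endpoint.** The Stage 2 safety endpoint (Protocol 7.2.2.2, SAP 2.3.2) names laboratory assessments and vital signs, alongside treatment-emergent AEs (TEAEs) and injection site reactions, as components compared with placebo.

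**The concern.** Routine Stage 2 samples are taken shortly before the next course or about four weeks after the last one. A laboratory change that rises and settles soon after a dose can be documented only by an unscheduled test or an early ET visit. Such tests are ordered because of the subject's condition, so they are the results most likely to show an acute effect, and the SAP keeps the unscheduled ones out of every laboratory summary. A subject with a documented abnormality that resolves before the next visit is tabulated as normal throughout.

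What is at stake is how the laboratory part of the comparison with placebo can be read. A reader of the Stage 2 shift table could take a row of normal-to-normal results as evidence against acute laboratory effects, when the table was not built to show them. Stage 1 does sample earlier, with Week 1 and Week 2 blood tests and a Day 1 rule of "On Day 1, vital signs assessments to be performed pre-dose and at 1-hour post-dose". But Stage 1 is single-dose and open-label with no placebo arm, so it cannot stand in for the repeat-dose comparison.

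**Working it through.** The plan states no figure of its own on this point, so there is none to reproduce. The check is schedule arithmetic followed by tracing where a result can appear.

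**Inputs** (Protocol Table 5 and sections 12.2.3, 12.2.4 and 12.2.6)
- Visits 3 to 5: 28 days after the previous visit, window 0 to +7 days, sample up to 4 days early.
- Visit 6: 28 days after Visit 5, window −7 to +7 days, sample up to 4 days early.
- ET visit: as soon as possible after withdrawal, at most 6 weeks (42 days) after the last dose, with no minimum interval.

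**Days from preceding dose to routine sample** = interval + visit window − early-collection allowance
- Visits 3 to 5: earliest 28 + 0 − 4 = 24; latest 28 + 7 − 0 = 35.
- Visit 6 after a course at Visit 5: earliest 28 − 7 − 4 = 17; latest 28 + 7 − 0 = 35.
- ET: 0 to 42.

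The earliest routine sample is therefore day 17 after a dose, which leaves days 1 to 16 unsampled. After courses one to three, when the next sample is at Visit 3, 4 or 5, the gap runs to day 23. If a course is cancelled for insufficient fat, Visit 6 falls on or after the cancelled visit, so the sample is no earlier than day 24. With 50 and 25 subjects and up to 4 courses each, the gap follows up to 50 × 4 = 200 active and 25 × 4 = 100 placebo courses.

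**Where a laboratory result can appear, by type**
- Scheduled visit: by-visit summary, out-of-range count, shift table and listing.
- Unscheduled, post-baseline: listing only.
- Repeat of a scheduled test: listing only; the first result is tabulated.
- ET visit: it shares the Visit 6 column in the schedule, but the SAP does not say how ET results are mapped in the tables.
- Any result that is clinically significant or accompanied by signs or symptoms, and meets the AE definition: also an AE under Protocol 14.2.5. It is then counted in the Stage 2 TEAE tables under SAP 11.1.

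**Worked case.** A subject is normal at baseline. An unscheduled test within 16 days of the Visit 3 course is high. The investigator judges it not clinically significant, there are no symptoms, and the Visit 4 sample is normal. The shift table records normal to normal, the out-of-range count at Visit 4 does not include the subject, and no AE is recorded. The high value is a line in Listing 16.2.8.1. The SAP table list (14.3.4.1.x and 14.3.4.2.x) contains no worst post-baseline table that would pick it up.

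**The case against.** The strongest reply is that the AE route already covers what matters. Findings that are clinically significant or symptomatic must be recorded as AEs if they meet the definition. Values that constitute a serious AE or lead to stopping the product must be too (Protocol 14.2.6). TEAEs run from first dose to end of study whatever the visit schedule, and are tabulated by arm. A marked hepatic or renal abnormality is the kind most likely to be called clinically significant, and related Grade 3 events of that kind can pause dosing under Protocol 8.4. Unscheduled tests are usually ordered because of the subject's condition, so the symptom route will often apply.

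This stands, and it rules out a stronger reading that a reader might infer: that acute abnormalities cannot appear in the safety comparison with placebo at all. They can, through the TEAE tables. What the AE route leaves uncovered is an abnormality that was measured, had no symptoms and was judged not clinically significant. That judgement rests with an investigator who is unblinded (Protocol 10.7).

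Three other inferences also go too far.
- The rule does not always understate harm. Tabulating the first result over the repeat keeps an abnormal first value, and dropping unscheduled placebo abnormalities can widen the apparent difference.
- The tables do not show only recovered values. Changes that persist or accumulate to the next visit are captured, and an early ET visit may sample close to a dose.
- The different post-dose vital-sign provisions in Stage 1 and Stage 2 are a design difference between stages with separate schedules and objectives. They are not a contradiction.

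It is also fair to say that the plan is descriptive and that unscheduled results are listed. Listings, however, give no by-arm count.

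**Conclusion.** The point holds in a limited form. For subjects seen in window, no routine Stage 2 laboratory or vital-sign collection falls in the first 16 days after any course. A transient laboratory abnormality found in that period on an unscheduled test and not reported as an AE is missing from the by-arm out-of-range counts and shift tables. The same table rule applies to vital signs, but SAP 11.3 specifies no out-of-range or shift table for them, so the practical consequence is confined to the laboratory tables. The use of unscheduled values for baseline is not a fault, since the protocol also defines baseline as the last available value before first treatment.

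How many subjects this affects cannot be estimated: the documents give no rate for unscheduled testing or for transient abnormalities. The conclusion assumes visits and samples within the stated windows. It sets aside ET visits, whose place in the tables is undefined. This is an inexpensive improvement to what the laboratory comparison with placebo can show. It does not mean that Stage 2 safety reporting as a whole is blind to acute events.

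**What to change.** In SAP 3.1 and 11.2:
- Keep the by-visit summaries, out-of-range counts and shift tables on scheduled values as they are.
- Add a by-arm worst post-baseline out-of-range and shift table for laboratory parameters, placed alongside Tables 14.3.4.2.x. Use scheduled, unscheduled, repeat and ET values, with the low and high directions taken separately.
- State how ET results are mapped to visits.
- Show days since last dose for the value that counts as worst.
- Add a table note giving the routine sampling times after dose, so that the scheduled tables are not read as acute post-dose safety.

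No change is needed to SAP 11.3 or 11.4 for this purpose.

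**Cost.** SAP wording and limited programming, from data already collected and listed; trial conduct does not change.

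**Downside.** A worst-value count depends partly on how often and when subjects are tested. Site staff who order extra tests know the allocation. Planned drop-out is also unequal: 16% of 50 = 8 on active and 44% of 25 = 11 on placebo, so the number and timing of scheduled and ET samples may differ by arm. The scheduled-only version should therefore be presented beside the new table. Neither version can recover changes that were never measured.
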